Study Protocol with Statistical Analysis Plan

Official Title:

Effectiveness of Augmented Reality as a Distraction Technique for Reducing Pain and Anxiety in Pediatric Dental Extractions: A Parallel-Group, Double-Blind Randomized Controlled Trial

NCT Number: NCT06954883

Unique Protocol ID: 17-2024-0004

Document Date: April 30, 2025

Author: [name]

Institution: Faculty of Dentistry, Assiut University Dental Hospital

1. Administrative Information

Principal Investigator: [name]

Institution: Faculty of Dentistry, Assiut University Dental Hospital

Trial Registration: ClinicalTrials.gov (NCT06954883)

Unique Protocol ID: 17-2024-0004

2. Background and Rationale

Pediatric dental anxiety and pain are common barriers to care.

Augmented Reality (AR) may reduce distress by immersive distraction.

Hypothesis: AR distraction will reduce pain and anxiety vs. Tell–Show–Do.

3. Objectives

Primary: To evaluate the effect of AR distraction on pain (Wong-Baker FACES).

Secondary: To evaluate effect on anxiety (CFSS-DS) and heart rate.

4. Study Design

Randomized, controlled, parallel-group, single-blind trial.

Setting: Pediatric Dentistry Clinic, Assiut University Dental Hospital.

5. Participants

Eligibility: Children aged 6–10 years, requiring tooth extraction, ASA I.

Exclusion: Visual/hearing impairment, neurological disorders, traumatic dental history.

6. Interventions

AR group: 30 children wore AR headset during anesthesia and extraction.

Control group: 30 children received Tell–Show–Do technique.

7. Outcomes

Primary: Pain (Wong-Baker FACES, 0–10).

Secondary: Anxiety (CFSS-DS, 15–75), Heart rate (bpm).

8. Sample Size Calculation

Based on 2-point difference in Wong-Baker scale, power 80%, alpha=0.05.

25 per group needed, increased to 30 per group (N=60).

9. Randomization and Blinding

Block randomization, sealed envelopes for allocation concealment.

Outcome assessors blinded to group allocation.

10. Statistical Analysis Plan

Analysis: Intention-to-treat. Significance $p<0.05$, two-sided.

Continuous data: Mean \pm SD, compared with t-tests (independent/paired).

Effect size (Cohen's d) calculated. Missing data <5% complete case.

Secondary outcomes analyzed similarly. Sensitivity analysis: per-protocol.

11. Ethics and Dissemination

Approved by Institutional Review Board, informed consent obtained.

Trial conducted per Declaration of Helsinki. Results to be published.

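### Age and extraction type are left in the error term of the primary pain comparison; adjusting for them would gain precision at almost no cost

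*Combined protocol and SAP*

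**What the plan says.** All references are to the combined protocol and SAP.

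- **Section 5 (Participants).** Entry: "Eligibility: Children aged 6–10 years, requiring tooth extraction, ASA I". Exclusions: "Exclusion: Visual/hearing impairment, neurological disorders, traumatic dental history". Neither line mentions tooth type, dentition, mobility or difficulty of the extraction, and neither mentions anesthesia.
- **Section 6 (Interventions).** "AR group: 30 children wore AR headset during anesthesia and extraction". The procedure studied therefore includes anesthesia, although Section 5 does not make it a condition of entry.
- **Section 7 (Outcomes).** The primary outcome is the Wong-Baker FACES score from 0 to 10. The time of rating is not given.
- **Section 8 (Sample Size Calculation).** "Based on 2-point difference in Wong-Baker scale, power 80%, alpha=0.05". This gives 25 per group, raised to 30. No SD is stated, nor any source or population for the 2 points.
- **Section 9 (Randomization and Blinding).** "Block randomization, sealed envelopes for allocation concealment". No stratification factor and no block size are given.
- **Section 10 (Statistical Analysis Plan).** Means are compared by t-tests, with "Significance $p<0.05$, two-sided". No covariate is named.

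**The concern.** The eligible extractions may differ a good deal in how much they hurt, and children of 6 and of 10 may use a faces scale differently. If so, part of the spread in the primary outcome can be predicted from facts available for each child: age, which is an entry criterion, and tooth type, which can be identified from the tooth removed. The plan uses neither, in allocation or in analysis.

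Two things are at stake. The confidence interval for the pain difference is wider than it need be. And with 30 per arm, a chance imbalance in age or tooth type can move the single estimate by a noticeable part of the 2 points the trial was sized for, with no planned analysis to take that shift out.

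**Working it through.** **Inputs from the documents.** Difference 2 points, power 80%, alpha 0.05 (Section 8); two-sided test (Section 10); 25 per group required and 30 planned (Section 8).

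**Inputs that are assumptions.** Prevalence p of one tooth type, 20% to 50%. Pain gap g between tooth types, 2 points. Share R² of pain variance explained by age and tooth type, 10% to 20%. The documents give none of these.

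**1. The plan's own sample size.** Without an SD, 25 per group cannot be reproduced directly, so I solve for the SD. With the noncentral t at 25 per arm and 80% power, the standardized difference is 0.809, so SD = 2 / 0.809 = 2.47. The normal approximation gives 2.52. An SD of 2.5 returns exactly 25 by the normal formula, so the stated size is consistent with an SD of about 2.5.

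**2. Precision and power as planned.** At 30 per arm:

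- SE = SD × √(2/30) = 2.47 × 0.258 = 0.64 points.
- Power for 2 points (noncentral t) = 86.9%.

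**3. Size of a chance imbalance.** The SD of the between-arm difference in proportions is √(p(1−p) × 2/30), and the 95% limit is 1.96 times that. The shift in the pain difference is the imbalance times g.

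| p | SD of imbalance | 95% limit | Shift at 1 SD, g = 2 | Shift at 95% limit, g = 2 |
|---|---|---|---|---|
| 20% | 0.103 | 0.202 | 0.21 | 0.40 |
| 50% | 0.129 | 0.253 | 0.26 | 0.51 |

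The exact hypergeometric probability that the arms differ by at least 20 percentage points is 10.4% at p = 20% and 19.6% at p = 50%.

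**4. Gain from adjustment.** The residual SD is SD × √(1−R²).

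| R² | Residual SD | SE at 30 per arm | Power for 2 points |
|---|---|---|---|
| 0 | 2.47 | 0.64 | 86.9% |
| 10% | 2.35 | 0.61 | 90.1% |
| 20% | 2.21 | 0.57 | 93.1% |

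Using 56 residual degrees of freedom in place of 58, for the two extra model terms, changes these powers by less than 0.1 percentage point. The R² range agrees with step 3: a 2-point gap alone explains p(1−p)g²/SD² = 0.64/6.12 = 10% at p = 20%, and 1.00/6.12 = 16% at p = 50%.

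**5. Validity of the planned test.** Trials were simulated with a 3-point gap, 20% or 40% easy extractions and a total SD of about 2.52. The unadjusted t-test under unstratified allocation kept its type I error at about 5%. For a uniform 2-point effect, adjusting for extraction type raised power from about 86% to 93% (20% easy) and from about 85% to 96% (40% easy). Stratifying the allocation without adjusting made the t-test conservative (type I error about 2% to 3%) and added almost no power.

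**The case against.** The strongest reply is that nothing here is an error. An unadjusted t-test after block randomization is valid. Chance imbalance is random error already counted in the standard error of 0.64. The 0.4 to 0.5 points is a 95% limit, and a typical shift is 0.21 to 0.26. On the plan's own figures the trial already exceeds 80% power. All of this stands, and it limits the point to precision.

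A reader might go further and infer that near-painless extractions, such as a loose milk tooth, dilute the 2-point effect and leave the trial underpowered. The documents do not support that as a finding. They give no case mix, no pain or AR effect by tooth type, and no time of rating. Section 6 includes anesthesia in the procedure, so an easy removal need not be a painless visit. Section 8 does not say which population the 2 points describe, so they may already refer to a mixed one. If AR had no effect in a share f of children and the SD stayed at 2.47, the difference would be 2(1−f), and power at 30 per arm would be 79%, 69% and 58% for f = 10%, 20% and 30%. Lower figures come only from adding between-type variance to an SD that Section 8 implies for the whole enrolled population.

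Two practical objections also have weight. The absence of stratification is inferred from silence in Section 9. And the past tense in Section 6 suggests that enrolment may be over, in which case changes to entry or allocation come too late and a late change of primary analysis could look post hoc. The second objection calls for a documented date of the change; it does not argue against adjustment.

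**Conclusion.** The point holds as a missed gain in precision. Entry does not classify the extraction, no stratification factor is named, and the primary comparison is unadjusted. Adjusting for age and tooth type would raise power from 87% to between 90% and 93%, and would remove the part of the estimate's movement that comes from imbalance in those two factors. These figures rest on the SD of 2.47 back-solved from Section 8 and on an assumed R² of 10% to 20%; if age and tooth type do not predict pain, the gain is nil and the loss negligible.

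It is not a finding of bias or of an inflated type I error, and it does not make the planned t-test invalid. Dilution of the 2-point effect remains possible but is not shown.

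**What to change.** **Section 10.** Make the primary analysis a linear model of the Wong-Baker score on group, age and tooth type (primary or permanent), reporting the adjusted mean difference with its 95% confidence interval. Keep the unadjusted t-test as a supporting analysis. Fix this before outcomes are compared by arm.

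**Section 9.** State whether any stratification factor was used. If randomization is still open and tooth type is added as a factor, pair it with the adjustment above.

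**Sections 5 and 6.** Reconcile the two on whether anesthesia is a condition of entry. Which way is for the investigators to decide.

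**Cost.** A line or two of SAP text, two model degrees of freedom, and recording tooth type or retrieving it from the dental record, since no section says it is collected. If data collection is finished, the SAP must also state, with a date, that the change preceded any unblinded comparison. No extra patients or visits are needed.

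### The plan describes no pre-procedure pain score and no baseline adjustment for the primary Wong-Baker comparison, which gives up precision that one entry rating could recover

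*Combined protocol and SAP*

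**What the plan says.** Section 7 gives the primary outcome as "Primary: Pain (Wong-Baker FACES, 0–10", that is, a scale and its range. It does not say when the child is asked, how often, or whether any rating precedes the procedure.

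Section 5 sets entry as "Eligibility: Children aged 6–10 years, requiring tooth extraction, ASA I". The exclusions are "Exclusion: Visual/hearing impairment, neurological disorders, traumatic dental history". Pain already present is neither required, excluded nor listed as recorded.

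Section 8 sizes the trial thus: "Based on 2-point difference in Wong-Baker scale, power 80%, alpha=0.05", and then "25 per group needed, increased to 30 per group (N=60". No SD is given.

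Section 9 names block randomization and no stratification factor.

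Section 10 says continuous data are "compared with t-tests (independent/paired". It does not say which outcome is paired or at which times, and it names no covariate-adjusted model. Secondary outcomes follow the same methods.

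**The concern.** The objective in Section 3 is the effect of AR distraction on pain. A single 0–10 face rating cannot separate pain that a child brought to the clinic from pain felt during anesthesia and extraction. If children differ in pain on arrival and this carries over into the later rating, three things follow:

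- The spread of the outcome is larger than it need be.
- With 30 children per arm, mean entry pain can differ between arms by chance.
- Without an entry score, that difference can be neither seen nor adjusted for.

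At stake is the width of the interval around the primary result, judged against a 2-point target.

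**Working it through.** **Inputs from the documents:** difference 2 points, power 80%, alpha 0.05 two-sided, 25 per group needed and 30 planned (Sections 8 and 10).

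**Assumed, because the documents give no figure:** a correlation r of 0 to 0.5 between entry score and post-procedure score.

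**1. The plan's own figure.** With no SD stated, 25 per group cannot be reproduced directly, so I solved for the SD that it implies. For a two-sample t-test (noncentral t, 48 df), 80% power at 25 per group needs a standardized difference of 0.809. The SD is then 2 / 0.809 = 2.47 points. The normal approximation gives 2.52. An SD of about 2.5 therefore makes Section 8 consistent.

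**2. The planned comparison at 30 per arm.**
- SE of the difference = 2.473 × √(2/30) = 0.639 points.
- 95% CI half-width = 2.002 × 0.639 = 1.278 points.
- Power for 2 points (58 df) = 86.9%.

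**3. With an entry score as covariate.** Residual SD = 2.473 × √(1 − r²), with 57 df.

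| r (assumed) | Residual SD | Variance removed | Power for 2 points | 95% CI half-width |
|---|---|---|---|---|
| 0 | 2.473 | 0% | 86.8% | 1.279 |
| 0.3 | 2.359 | 9% | 89.8% | 1.220 |
| 0.5 | 2.142 | 25% | 94.5% | 1.107 |

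The r = 0 row shows the price of a useless covariate: 0.001 points of half-width.

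**4. Chance imbalance, on the outcome scale.** An imbalance in entry pain reaches the outcome through the regression slope, so the SE of the shift is r × 2.473 × √(2/30).
- r = 0.3: SE 0.19 points; 95% range 1.96 × 0.192 = ±0.38 points.
- r = 0.5: SE 0.32 points; 95% range 1.96 × 0.319 = ±0.63 points.

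This is the same variance that is removed in step 3 (at r = 0.5, 0.319² / 0.639² = 0.25), so the two gains must not be added.

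**5. Why not a change score.** If the two scores have equal SDs, the change score has variance 2(1 − r) times that of the post-procedure score: 1.4 at r = 0.3 and 1.0 at r = 0.5. Below r = 0.5 it loses precision against the plain t-test. ANCOVA does not, apart from the one degree of freedom.

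**The case against.** The strongest reply is that the documents do not say that a pre-procedure score is absent. A paired t-test in a parallel-group trial needs two readings per child, so Section 10 implies that some outcome is measured repeatedly, and pain is not ruled out. This stands: a reader might infer that no entry score is taken, but the text is only silent. It does not remove the point. A paired test within an arm does not compare AR with control, and no section brings an entry score into the between-arm comparison.

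Three further inferences go beyond the documents:

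- **That toothache contaminates or biases the result.** Needing an extraction does not establish pain on arrival, no prevalence is given, and randomization protects the comparison on average.
- **That chance imbalance threatens half the target.** With an assumed entry-pain SD of 2.0 to 3.0 points, the arms would differ by more than 1 point in mean entry pain in 5% to 20% of trials (SE 0.52 to 0.77). That is imbalance at entry, not in the outcome. At r of 0.3 to 0.5 the shift in the outcome exceeds 1 point in under 0.2% of trials (at r = 0.5, 1 / 0.319 = 3.1 standard errors). It is also already counted in the unadjusted confidence interval.
- **That the trial is underpowered.** The implied SD may already include variation in entry pain, and on it 30 per arm exceeds the 80% target.

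The reply that the gain is modest also stands in part. At r = 0.3 it is about 3 percentage points of power, and if pain is rated under anesthesia the correlation could be low.

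**Conclusion.** The point holds as an improvement in precision, not as a flaw in validity. The plan describes no pre-procedure pain rating and no baseline adjustment for its primary outcome, and it leaves the timing of pain and the role of the paired test undefined.

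At an outcome SD of 2.47 and r between 0 and 0.5, adjustment moves power at 30 per arm from 87% to between 87% and 94%, and the half-width from 1.28 to between 1.28 and 1.11 points. The gain rests wholly on an assumed correlation and a back-solved SD. It is nil at r = 0, small at 0.3 and worthwhile at 0.5. Because the cost is also very small, the change is worth making if it is still possible.

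**What to change.** In Section 7, state when pain is rated. Add one Wong-Baker score for every child in both arms, taken before allocation is revealed and hence before Tell–Show–Do or the headset could affect it. If such a score is already collected, say so.

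In Section 10, make the primary analysis an ANCOVA of the post-procedure score on arm and entry score. Report the adjusted difference in points with its 95% CI. Say which outcomes the paired tests concern, and that within-arm tests are not evidence of a difference between arms.

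The cost is one more question per child on a scale already in use, one degree of freedom, and a sentence or two in each section.

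Section 6 describes the interventions in the past tense, so enrolment may be over. If it is and no entry score exists, keep the planned unadjusted comparison and report as a limitation that entry pain was not measured. Adjusting for age is no substitute: age does not measure entry pain, the documents give no correlation between age and pain, and adding it now could be a post hoc change to the primary analysis.

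### Paired t-tests in Section 10 cannot test AR versus Tell-Show-Do and should be descriptive only; if CFSS-DS or heart rate has a pre-technique value, ANCOVA would be more precise than the listed t-tests

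*Combined protocol and SAP*

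**What the plan says.** All references are to the combined protocol and SAP.

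- Section 10 has continuous data summarised by mean and SD and "compared with t-tests (independent/paired"). It does not say which comparison each test serves. It adds "Secondary outcomes analyzed similarly" and "Effect size (Cohen's d) calculated". No covariate-adjusted analysis is mentioned.
- Section 2 gives the only hypothesis: "Hypothesis: AR distraction will reduce pain and anxiety vs. Tell–Show–Do". Section 4 gives the design: "Randomized, controlled, parallel-group, single-blind trial".
- Section 7 lists the other outcomes: "Secondary: Anxiety (CFSS-DS, 15–75), Heart rate (bpm"). No measurement time and no baseline value is stated for them or for pain.
- Section 6 says "AR group: 30 children wore AR headset during anesthesia and extraction".
- Section 8 sizes the trial on pain alone: "Based on 2-point difference in Wong-Baker scale, power 80%, alpha=0.05".

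**The concern.** In a parallel-group trial the two arms hold different children, so pairing can only mean two values from one child. A paired t-test then measures change within an arm. That change mixes any AR effect with the passage of time, procedural stress and regression to the mean, and it does not answer a between-arm hypothesis.

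Two things are at stake, of different kinds. The first is interpretation. The official title claims both pain and anxiety, and with two tests listed and no roles assigned, a significant fall in the AR arm without one in the control arm could be offered as an AR effect. The second is precision. If a value is taken before either technique begins, neither listed test makes the best use of it. The choice between testing the outcome value and testing the change would also stay open, and which of those is more precise depends on a correlation not known in advance.

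**Working it through.** **The plan's own figure.** The only one is the 25 per group in Section 8. It concerns pain and cannot be reproduced because no SD is given. The two-sided normal formula gives 2 × (1.96 + 0.84)² × SD² / 2², which rounds up to 25 at an assumed SD of 2.5. Nothing below depends on it.

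**Inputs.** From the document: 30 per arm, two-sided alpha 0.05. Assumed, because the document gives neither: a correlation r between baseline and outcome of 0.3, 0.5 or 0.7, and the size of any change common to both arms. No SD is given for CFSS-DS or heart rate, so results are in outcome SDs unless stated. All 60 children are taken as analysed.

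**Precision, if a pre-technique value exists.** The half-width of the 95% CI for AR minus Tell-Show-Do is t × √(2/30) × f, with √(2/30) = 0.258.

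- Outcome-value t-test: t = 2.002 (58 df), f = 1.
- Change-score t-test: t = 2.002 (58 df), f = √(2(1 − r)).
- ANCOVA: t = 2.002 (57 df), f = √(1 − r²) × √(1 + 1/56). The last factor allows for chance baseline imbalance.

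| | r = 0.3 | r = 0.5 | r = 0.7 |
|---|---|---|---|
| Half-width, outcome value | 0.52 | 0.52 | 0.52 |
| Half-width, change score | 0.61 | 0.52 | 0.40 |
| Half-width, ANCOVA | 0.50 | 0.45 | 0.37 |
| Detectable at 80% power, outcome value | 0.74 | 0.74 | 0.74 |
| Detectable at 80% power, change score | 0.87 | 0.74 | 0.57 |
| Detectable at 80% power, ANCOVA | 0.71 | 0.64 | 0.53 |

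The detectable differences use the noncentral t with the same f. Leaving out the small imbalance factor, the ANCOVA variance is 1 − r² of the outcome-value variance (9%/25%/49% lower) and (1 + r)/2 of the change-score variance (35%/25%/15% lower). ANCOVA gives the narrower interval than the outcome-value test once r exceeds about 0.14, and than the change-score test for r below about 0.96. At r = 0 it is 0.522 against 0.517, about 1% wider. In simulation its type I error was 0.049 to 0.051.

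**Interpretation, only if within-arm p-values were used for the AR claim.** Suppose there is no AR effect and both arms improve by d SDs of the within-child change. Let p be the chance that a paired t-test with 30 children (29 df, noncentrality d√30) is significant. The arms are independent, so the chance of significant improvement in AR and no significance in control is close to p(1 − p). This cannot exceed 0.25, reached at p = 0.5, that is d = 0.37. Counting only improvement in the AR arm, the rate is 2.4% at d = 0, 15% at 0.2, 25% at 0.37, 19% at 0.5 and 1.1% at 0.8.

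The SD of the change equals √(2(1 − r)) outcome SDs, so the peak lies at 0.37 × 1.183/1.000/0.775 = 0.44/0.37/0.29 outcome SD for r = 0.3/0.5/0.7. A common change of 0.5 outcome SD gives 24%/19%/7%. In simulation at the peak, about 91% of the trials showing this pattern had a non-significant independent t-test on the change, and 93–94% a non-significant one on the outcome value.

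**The case against.** The strongest reply is that no error is shown. Sections 2, 4 and 8 all point to a between-arm test, the independent t-test holds its 5% level, and no sentence offers paired p-values as support for AR. That stands: the role of the paired test is left open, and no wrong inference is planned.

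It also stands that no baseline is documented. The only clue to repeated values is the word paired in a one-line list of tests, and it may be boilerplate with no repeated measurement behind it. The ANCOVA advice is therefore conditional. At r = 0.3 the gain is small, 0.52 to 0.50 SD.

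A third reply is that the paired wording covers all continuous data, so pain should not be exempt. That is correct for the role of paired tests, which should be descriptive for any outcome. It does not bring ANCOVA to pain: no pre-technique pain score is documented, and the independent t-test serves the primary outcome.

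A reader might infer that the trial has a false-positive rate of 25%, or that it collects a baseline and ignores it. The document supports neither. The 25% is a ceiling under a decision rule that the plan does not state, at one size of common change, and nothing in the document places the trial there. Whether a baseline is collected is simply not said.

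**Conclusion.** This is a cheap improvement, not a validity failure of the planned between-arm test. Two parts hold. First, paired comparisons cannot test the stated hypothesis and need an explicit descriptive role; this does not depend on any assumed figure. Second, if CFSS-DS or heart rate is recorded before either technique begins, ANCOVA narrows the interval from 0.52 SD to between 0.50 and 0.37 SD, and it beats the change-score test at each r tried. The size of that gain rests on the assumed r and on a baseline that the document does not mention. The test of pain and the sample size are unaffected.

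**What to change.** Keep the mean and SD by arm in Section 10 and add:

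> All hypotheses are tested by AR versus Tell-Show-Do. Pain: independent t-test. CFSS-DS is analysed at [one named time] and heart rate at [one named time]. If a value is collected before either technique begins, the analysis is ANCOVA of the outcome at that time on treatment and the baseline value; otherwise it is an independent t-test. Values taken during the procedure are not used as baseline. The mean difference with 95% CI is reported with Cohen's d. Paired comparisons, for any outcome, are descriptive only and are not evidence of an AR effect.

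The line on procedural values guards the new model; it does not correct anything in the plan. The headset is worn through anesthesia and extraction, so a reading at the first stage is already on treatment. With an equal effect of 0.5 SD at both stages (assumed), adjusting for it would shrink the expected estimate to 0.5 × (1 − r) = 0.35/0.25/0.15 SD at r = 0.3/0.5/0.7.

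The cost is naming two measurement times and, where a baseline exists, one regression and one degree of freedom per secondary outcome. Section 6 is written in the past tense. If data have already been collected, make the change as a dated, disclosed amendment and show the independent t-test beside the ANCOVA.

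### Do unassigned paired t-tests and missing measurement times leave the primary pain comparison undefined?

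*Combined protocol and SAP*

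**What the plan says.** Five places bear on the point, all in the combined protocol and SAP.

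- **Section 10** says continuous data are "compared with t-tests (independent/paired", two-sided at 0.05. Secondary outcomes are to be handled in the same way.
- **Section 7** names one primary, "Primary: Pain (Wong-Baker FACES", scored 0–10. CFSS-DS anxiety and heart rate are secondary. Each has a scale or unit only.
- **Section 2** states the hypothesis as "AR distraction will reduce pain and anxiety" relative to Tell–Show–Do. The title also names both outcomes: "for Reducing Pain and Anxiety in Pediatric Dental Extractions".
- **Sections 4 and 6** describe the design as "Randomized, controlled, parallel-group, single-blind trial" and report that "30 children wore AR headset during anesthesia and extraction".
- **Section 8** gives "Based on 2-point difference in Wong-Baker scale, power 80%, alpha=0.05", then "25 per group needed, increased to 30 per group (N=60".

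**The concern.** Section 9 describes block randomization and no matching, so a paired t-test here can only compare two readings on one child. Section 7 defines no second reading for any outcome. If paired tests are really intended, something is measured twice, and the plan does not say what, when, or whether groups are compared on the later score or on the change. The headset is worn through two painful steps, and the 2-point difference in Section 8 is tied to neither.

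Two things would be at stake. First, the choice between later score and change score affects power. Made after seeing results, it also raises the chance of a false finding in favour of AR. Second, a within-arm paired test does not compare AR with Tell–Show–Do. A significant fall in one arm and not in the other can arise from a fall common to both arms, with no AR effect at all.

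**Working it through.** **1. Which test does the plan lead to for pain?** Set the sections side by side.

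| Element | Where | What it implies |
|---|---|---|
| One primary outcome, Wong-Baker | 3, 7 | One primary test |
| Hypothesis against Tell–Show–Do | 2 | Comparison between arms |
| Parallel groups, block randomization, no matching | 4, 9 | Arms are independent samples |
| 2-point difference, 25 then 30 per group | 8 | Two-group sizing |
| Independent t-test available, two-sided 0.05 | 10 | Test and level |

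The only test that answers the Section 2 hypothesis with this design is the independent t-test on Wong-Baker. No section mentions a pre-procedure pain rating.

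**2. Does the sample size fit that test?** The documents give no SD, so 25 cannot be derived from their inputs alone, but the SD it implies can be. With the noncentral t distribution, 25 per group, two-sided 0.05 and 80% power:

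- standardized difference d = 0.809
- SD = 2 / 0.809 = 2.47 points
- power with 30 per group at the same d = 86.9%

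The normal approximation n = 2(1.960 + 0.842)² × SD² / 2² gives 24.5, rounded up to 25, at an assumed SD of 2.5. At assumed SDs of 2.0, 3.0 and 3.5 it gives 16, 36 and 49. So 25 fits a two-sided comparison between arms if the SD is about 2.5. This is consistent with that contrast but does not prove it.

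**3. What would the later-score or change-score choice cost?** This applies only to an outcome measured twice. As an illustration, take d = 0.809 on the later score, equal SDs at both readings and an assumed within-child correlation r. The change score has d / √(2(1 − r)). The later score adjusted for the earlier one has about d / √(1 − r²). Power with 30 per group:

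| r | Later score | Change score | Adjusted later score |
|---|---|---|---|
| 0.3 | 87% | 74% (d = 0.683) | 90% |
| 0.5 | 87% | 87% (d = 0.809) | 94% |
| 0.7 | 87% | 98% (d = 1.044) | 99% |

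Picking the better of later and change score after the fact, with no true effect, gives an AR-favouring error of 4.4% to 4.6% by simulation, against 2.5% for one fixed test.

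**4. What if two paired tests were read as the comparison?** Let p be the chance that one arm of 30 shows a significant fall. With no AR effect, the chance of a significant fall with AR only is p(1 − p). At assumed r = 0.5 the SD of the change equals the SD of one reading, since √(2(1 − 0.5)) = 1.

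| Shared fall (SD) | p | p(1 − p) |
|---|---|---|
| 0 | 2.5% | 2.4% |
| 0.3 | 35.5% | 22.9% |
| 0.5 | 75.4% | 18.6% |
| 0.7 | 95.9% | 3.9% |
| 0.8 | 98.8% | 1.1% |
| 1.0 | 99.96% | 0.04% |

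The quantity cannot exceed 0.5 × 0.5 = 25%. It is large only for moderate shared falls and vanishes when both arms fall clearly.

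**The case for a change.** The strongest case for a change is that inference is not specification. The intent to compare arms can be read from the plan, but the step at which pain is scored cannot, nor can the role of the paired tests. Two analysts could both comply and report different pain results. A few sentences would remove the doubt, with no added children and no loss of power.

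Part of this stands. Section 7 gives no time for any outcome, Section 10 does not assign the paired test, and a report of the trial should state both.

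The rest carries less weight. The wording in Section 10 can be read as a generic list of tests to be used where they apply. If a repeat reading exists, nothing places it on pain. On CFSS-DS or heart rate the ambiguity falls on a secondary outcome and leaves the primary test untouched. Nothing in the documents suggests that the AR effect differs between anesthesia and extraction, so a smaller effect at one step would be pure supposition. Anxiety appears beside pain in the title and hypothesis, but Sections 3 and 7 rank it as secondary, so an either-or claim would contradict the plan.

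Simply requiring the later score would be no better method than the plan already allows: at r = 0.7 it gives 87% power against 98% for the change score. Adjusting for an earlier reading does better, but it presupposes a baseline that the plan does not describe.

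**Conclusion.** The gap is real but is one of missing detail. An analyst following this plan would compare Wong-Baker scores between arms with an independent two-sided t-test at 0.05. That is a sound test with 5% error and, at the SD of 2.47 implied by 25 per group, 87% power with 30 per group analysed.

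The adverse figures are conditional on choices the documents do not make. The 4.4% to 4.6% error needs a repeat reading and a choice made after seeing results. The error of up to 25% needs separate paired tests to replace the comparison stated in Section 2, and it also depends on the size of an assumed shared fall. The power differences need an assumed correlation and an effect size borrowed from pain.

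Section 6 is written in the past tense, so the measurement times may already be settled by what was done. They can be stated in the report, with any later analytic choice labelled post hoc. No change to the plan follows.

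### Does analysing the Wong-Baker pain score only by t-test cost the primary comparison power if many AR children choose the lowest face?

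*Combined protocol and SAP*

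**What the plan says.** Section 7 names the primary outcome as "Primary: Pain (Wong-Baker FACES, 0–10"). It does not state how many faces there are or the step between them.

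Section 10 gives one method by data type. Continuous data are summarised by mean and SD and "compared with t-tests (independent/paired"), at a two-sided 5% level. It adds "Effect size (Cohen's d) calculated". It names no rank or ordinal method, no check of the distribution and no fallback. "Sensitivity analysis: per-protocol" is the only sensitivity analysis, and it changes the population, not the method. Section 10 does not expressly class pain as continuous, but it offers nothing else for it.

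Section 8 sizes the trial on a difference in points: "Based on 2-point difference in Wong-Baker scale, power 80%, alpha=0.05", leading to "25 per group needed, increased to 30 per group (N=60"). It gives no SD and no expected distribution of scores.

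**The concern.** A face scale takes a few ordered values and has a hard lower limit. The trial's hypothesis is that AR lowers pain, so many AR children could end at the lowest face. The scores would then be skewed and tied, and textbook advice is to use a rank or ordinal method. If that advice applied here, the primary comparison would lose power just when AR succeeds in moving children to no pain. Cohen's d would divide by an SD distorted by the floor, and nothing reported would say how many more children had little pain.

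A case that supports this is easy to build. With 60% of AR and 30% of control children at the lowest face, one set of assumed distributions gives about 55% power by t-test and 67% by rank-sum. With 50% against 20%, another gives about 64% against 71%.

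**Working it through.** **Inputs.** From the document: score range 0 to 10 (Section 7); 2-point difference, 80% power, 25 per group raised to 30 (Section 8); two-sided 5% level and t-test (Section 10). Assumed, because the document is silent: six faces scored 0, 2, 4, 6, 8, 10, and every response distribution below.

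**1. The plan's own figure.** n per group = 2·SD²·(1.960 + 0.842)² / difference². No SD is stated, so 25 can only be back-solved: SD = 2·√(25/2)/2.802 = 2.52. With an assumed SD of 2.5, n = 2·6.25·7.85/4 = 24.5, rounded up to 25. SDs of 2.0 and 3.0 would give 16 and 36. The calculation concerns a difference in means, which is what the t-test tests.

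**2. Validity.** With identical distributions in both arms and 10% to 50% of children at the lowest face, the t-test rejects in 0.048 to 0.053 of runs (30 per arm, 20,000 runs). The rank-sum test behaves the same. The floor does not inflate false positives.

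**3. Does a pile-up favour the rank test?** Power at 30 per arm, 20,000 runs:

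| Assumed mechanism | AR at lowest face | t-test | Rank-sum |
|---|---|---|---|
| Normal scores (SD 2.5, shift 2), rounded and censored | 34% | 0.825 | 0.817 |
| | 66% | 0.768 | 0.764 |
| | 79% | 0.695 | 0.694 |
| Proportional-odds shift (log OR 1.3) | 29% | 0.782 | 0.793 |
| | 66% | 0.688 | 0.747 |
| | 79% | 0.589 | 0.669 |
| 40% of AR moved to the lowest face, rest as control | 46% | 0.654 | 0.710 |
| | 52% | 0.492 | 0.616 |
| | 61% | 0.347 | 0.463 |
| Floor in AR, about 10% of AR still at 10 | 60% | 0.836 | 0.952 |
| | 60% | 0.531 | 0.817 |
| | 70% | 0.397 | 0.857 |

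At the same 79% floor, the gap is nil under censoring and 8 points under proportional odds. Under censoring both tests lose power together because the difference itself is compressed, so changing the test recovers nothing.

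**4. Can the direction reverse?** Yes, when AR also thins out the high scores. The probabilities run over faces 0, 2, 4, 6, 8, 10 (8,000 runs), and each mean is the sum of face × probability:

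| AR | Control | Means, difference | t-test | Rank-sum |
|---|---|---|---|---|
| .60 .30 .10 0 0 0 | .30 .30 .25 .10 .05 0 | 1.0 vs 2.6, 1.6 | 92% | 86% |
| .60 .35 .05 0 0 0 | .30 .35 .10 .10 .10 .05 | 0.9 vs 3.0, 2.1 | 97% | 88% |
| .60 .20 .12 .06 .02 0 | .30 .25 .20 .13 .08 .04 | 1.4 vs 3.12, 1.72 | 75% | 74% |
| .50 .30 .15 .05 0 0 | .20 .25 .25 .15 .10 .05 | 1.5 vs 3.7, 2.2 | 95% | 91% |

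The first three rows have 60% against 30% at the lowest face and the fourth has 50% against 20%. These are the floor shares at which the t-test could be made to look weaker. Here it is 1 to 9 points stronger.

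**5. What decides it.** The rank test gains clearly when a tail of high scores remains in the AR arm. The t-test gains when AR shortens that tail. The share at the lowest face does not tell the two apart.

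**The case for a change.** The strongest reply is that the stakes are lopsided. In the first table the rank test is never more than about 1 point worse, and it is up to 46 points better (0.857 − 0.397). The mechanism in which some children move to no pain while the rest stay as they were fits distraction well, and it favours the rank test by about 6 to 12 points. Naming a rank test in the SAP would be cheap insurance.

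Those figures stand for the distributions that produced them. The asymmetry does not survive the second table, where the rank test costs up to 9 points in cases whose differences are close to the planned 2. Neither set of distributions comes from the document, so the preference rests on a guess about how AR works. Making the rank test primary would also separate the test from the difference in points in Section 8. And Section 6 describes the interventions in the past tense; if data already exist, replacing the primary test carries a risk of its own.

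On reporting, it is true that Cohen's d is awkward for a bounded score and that no count of children per face is planned. But Section 10 also reports each arm's mean and SD, so the difference can be set directly against 2 points without d. A table of faces by arm, or a rank or ordinal sensitivity analysis, would be a reasonable addition, but its absence makes no planned result wrong.

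**Conclusion.** The concern does not hold. At 30 per arm the planned t-test keeps type I error near 5% and tests the quantity on which the trial was sized. Its power relative to a rank-sum test ranges from 9 points better to 46 points worse across the assumed distributions, with no difference under simple censoring. The range reflects whether high scores persist in the AR arm, not how many children are at the lowest face. The document gives no SD, score distribution or number of faces from which to choose among these cases, so a power loss cannot be called a property of the plan. The choice between the two tests is one on which reasonable statisticians differ. All power figures rest on the assumed six faces and the assumed distributions. The type I error result covers identical distributions in the two arms with up to 50% at the lowest face.
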